7.1.3 Electrocardiogram Withdrawal Criteria

All ECGs conducted or overread after a patient has been randomized will be subject to ECG Withdrawal Criteria (Section 11.5). Patients may be discontinued from blinded study medication if they experience a significant abnormality(ies) on their ECG including, but not limited to those listed in the ECG Withdrawal Criteria, Section 11.5, and in consideration with the patient’s medical history and baseline ECG measurements. Clinically significant abnormalities as determined by the Investigator may also result in patient discontinuation from study medication per the Investigator’s judgement. Triplicate ECGs (over a brief period of time) should be performed on patients experiencing a

significant abnormality on their ECG or other clinically significant abnormality as determined by the Investigator. The intent of triplicate ECG measurements is to differentiate significant abnormalities from artifact. Abnormalities should be confirmed in 2 of 3 triplicate ECG measurements.

7.1.4 COPD Exacerbation Withdrawal Criteria

Guidelines for identifying COPD exacerbation in this study and conditions for study continuation or withdrawal due to COPD exacerbation can be found in Section 11.6.

7.1.5 Positive Pregnancy Test in Females

Women who are pregnant or breastfeeding are not eligible to participate. Pregnancy testing is being conducted in women of childbearing potential at Screening and at other times specified in the SoA (Section 1.3).

Women exhibiting a positive pregnancy test (Section 11.3) during the study will be discontinued from blinded study medication and followed-up per the Collection of Pregnancy Information guidelines in Section 8.7.5 and Section 11.8.

7.1.6 Positive COVID-19 Test Indicating an Active Infection

Patients with a positive COVID-19 test result indicating an active infection will be required to discontinue blinded study medication and will be required to withdraw from the study.

7.1.7 Other Criteria

Other criteria that may or may not require permanent discontinuation of blinded study medication include but are not limited to adverse event, lack of efficacy, protocol deviation, non-compliance, study closed/terminated, investigator discretion or patient withdrawal of consent.

7.2 Study Participation After Discontinuation of Blinded Study Medication

Patients may permanently discontinue blinded study medication before the end of the study if they choose to or at the investigator's discretion.

Patients who permanently discontinue blinded study medication are not required to withdraw from the study unless they test positive for COVID-19 active disease. Patients who have permanently discontinued blinded study medication but do not test positive for COVID-19 active disease and have not withdrawn consent may continue in the study and complete all remaining protocol specified visits.

The Investigator must document the reason for discontinuation of blinded study medication in the eCRF.

Ideally, patients who have permanently discontinued blinded study medication will continue to attend scheduled clinic visits and complete important efficacy and safety assessments. However, if this is not possible then the investigator will encourage the patient to select one of the three options below to participate in as much of the study as they are willing (or able) to participate:

7.2.1 Reduced Assessments

The patient continues to follow the SoA (Section 1.3) and completes only the following assessments:

- Spirometry
- SGRQ
- COPD exacerbation
- AE
- Concomitant medication

7.2.2 Combination of Phone Contact and Reduced Assessments

The site contacts the patient by phone per the SoA (Section 1.3) to complete the following assessments:

- COPD exacerbation
- SAE
- Concomitant medication

In addition, the patient returns to the clinic at Week 24 to complete the following assessments:

- Spirometry
- SGRQ
- COPD exacerbation
- SAE
- Concomitant medication

7.2.3 Phone Contact Only

The site contacts the patient by phone per the SoA (Section 1.3) to complete the following assessments:

- COPD exacerbation
- SAE
- Concomitant medication

7.3 Patient Discontinuation/Withdrawal from the Study

A patient may withdraw from the study at any time at his/her own request, may permanently discontinue blinded study medication but wish to remain in the study, or may be withdrawn from administration of blinded study medication or from all study participation at the discretion of the Investigator at any time for safety, behavioral, compliance, or administrative reasons. See the SoA (Section 1.3) for data to be collected at the time of study discontinuation and follow-up and for any further evaluations that need to be completed.

- If the patient withdraws consent for disclosure of future information, the Sponsor may retain and continue to use any data collected before such a withdrawal of consent.
- If a patient withdraws from the study, he/she may request destruction of any samples taken and not tested, and the Investigator must document this in the study center study records.

7.3.1 Early Termination/Withdrawal Procedures

If a patient is withdrawn prior to the Week 12 visit, every attempt should be made to have the patient complete the early termination/ withdrawal procedures in the SoA (Section 1.3) as soon as possible.

- If possible, patients should remain on blinded study medication and their maintenance LAMA or LABA medication and ICS (if applicable), follow the withholding procedures prior to Spirometry in Section 8.3.1.2, and should refrain from smoking or caffeinated beverages as recommended in Section 5.4.1.1.
- Patients unable to remain on blinded study medication and/or their maintenance LAMA or LABA medications and ICS (if applicable) should still complete the early termination/ withdrawal visit as soon as possible.

7.3.1.1 12-Hour Spirometry and 1.5 Hour ECG Procedures

For patients who are withdrawn prior to completing the Week 12 visit only, every attempt should be made to have the patient complete the 12-hour spirometry procedures and the ECG procedures at the early termination/withdrawal visit unless consent is withdrawn or the patient is being withdrawn for safety reasons precluding this assessment.

Patients who Continued Blinded Study Medication

Patients who have continued administration of their blinded study medication should complete the spirometry and ECG procedures as follows:

- Spirometry: Pre-dose and 0-12-hour post-dose assessments as per Section 1.4 and Section 8.3.1.
- ECG: Pre-dose and 1.5-hour post-dose ECG procedures as per Section 8.4.2.

Patients who Discontinued Blinded Study Medication

Patients who have discontinued blinded study medication prior to the early termination/withdrawal visit may optionally complete spirometry and ECG assessments at the early termination visit if they have not already completed the Week 12 assessments. These patients will not be dosed with blinded study medication. If possible, patients should start spirometry between 6 am and 10am, withhold rescue medication and/or maintenance LAMA or LABA medications for the time period specified in Section 6.7.2, and refrain from caffeinated beverages and/or smoking for the time period specified in Section 5.4.1. The spirometry and ECG procedures should be completed as follows:

- Spirometry: Serial spirometry at 0-hour, 30 min, and 1, 2, 4, 6, 8, and 12 hours.
- ECG: 12-lead ECG at 0-hour and 1.5 hours.
- Note: If a patient completed only one of the serial 12-hour spirometry or 1.5-hour ECG procedures at Week 12, they may optionally complete the other one (the one not completed at Week 12) at this visit.

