7.0 DISCONTINUATION OF BLINDED STUDY MEDICATION AND PATIENT DISCONTINUATION/WITHDRAWAL

7.1 Discontinuation of Blinded Study Medication

Patients who permanently discontinue blinded study medication are not required to withdraw from the study unless they test positive for COVID-19 active disease. If a patient must permanently discontinue blinded study medication for reason(s) other than testing positive for COVID-19 active disease, the patient should complete the “Patient Discontinuation/Withdrawal from the Study” assessments described in Section 7.3 as soon as possible. In addition, every effort should be made by the investigator/staff to keep the patient in the study to collect important efficacy and safety data as detailed in Section 7.2.

Circumstances potentially requiring or actually resulting in discontinuation of blinded study medication are described below.

See the SoA (Section 1.3) for data to be collected at the time of treatment discontinuation and follow-up and for any further evaluations that need to be completed.

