9.4 Statistical Analyses

9.4.1 Efficacy Analyses

Efficacy analysis will primarily be performed on the mITT population. The primary endpoint and key secondary endpoints will also be evaluated using the PP population as a sensitivity analysis. Impact of imputations and various baseline characteristics will also be checked.

The primary endpoint, change from baseline in FEV₁ AUC_{0-12h} at Week 12, will be compared between treatments using an analysis of covariance (ANCOVA) model adjusting for treatment, region, background medication strata, and smoking status as factors and baseline FEV₁ as covariate. The estimated treatment difference with 95% confidence interval and associated (two-sided) p-value will be presented. Missing data will be imputed to get as close to the mITT population as possible. Primarily imputation will be based on data collected at visits performed after treatment withdrawal or at early termination visits even if outside visit window. When no such data is available, imputation will primarily be done using multiple imputation based on baseline characteristics and secondarily, as a sensitivity analysis, by the average change in the opposite treatment group as randomized to as a worst-case scenario. Further details on the handling of missing data will be given in the Statistical Analysis Plan.

Key secondary endpoints, FEV₁ AUC_{0-4h}, peak FEV₁, morning trough FEV₁, SGRQ total score and weekly mean E-RS total score, and other continuous secondary or exploratory endpoints will be assessed repeatedly during the study and the change from baseline to pre-specified time point of evaluation will be compared by similar ANCOVA models adjusting for treatment, region, background medication strata and smoking status as factors and baseline as covariate. Data collected at visits performed after treatment withdrawal or at early termination visits will be used in the analyses. Remaining missing data will primarily be imputed using multiple imputation based on baseline characteristics and data collected at post-randomization visits. Since assessed repeatedly, in contrast to primary endpoint, these data will also be analyzed for sensitivity by mixed model repeated measures models with treatment, visit and treatment by visit interaction as factors, baseline as covariate, subject as random factor and covariance structure by visit.

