2.5. ESTIMANDS

The primary and secondary estimands to support regulatory decisions are described in Table 1.

Table 1: List of Estimands

		Attributes			
Estimand	Definition	Population	Variable/ Endpoint	Intercurrent event handling strategy	Population-level summary measure
Primary	The efficacy of ensifentrine on lung function compared to placebo over a 12-hour dosing interval in patients with moderate to severe COPD.	Patients with moderate to severe COPD aged 40-80 years (inclusive) that are in the modified intent-to-treat (mITT) population. See full list of inclusion and exclusion criteria in sections 5.1, 5.2 and 5.3 of study protocol.	Change from baseline forced expiratory volume in 1 second (FEV ₁) to average FEV ₁ area under the curve over 12 hours (AUC _{0-12h}) at Week 12.	Regardless of whether the patient discontinues treatment prematurely and regardless of major protocol deviation, as per the Treatment Policy strategy.	Estimated treatment difference at Week 12 of the double-blind period (and corresponding 95% confidence interval [CI]) from analysis of covariance (ANCOVA) analysis.
Secondary	To evaluate the effect of ensifentrine on other lung function parameters.	Patients with moderate to severe COPD aged 40-80 years (inclusive) that are in the mITT population. See full list of inclusion and exclusion criteria in sections 5.1, 5.2 and 5.3 of study protocol.	
 Change from baseline FEV₁ to average FEV₁ AUC_{0-4h} at Week 12 Change from baseline FEV₁ to peak FEV₁ at Week 12 Change from baseline FEV₁ to morning trough FEV₁ at Week 12 	Regardless of whether the patient discontinues treatment prematurely and regardless of major protocol deviation, as per the Treatment Policy strategy.	Estimated treatment difference at Week 12 of the double-blind period (and corresponding 95% CI) from ANCOVA analysis.

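### Protocol 7.3.1.1 asks for every attempt at 12-hour spirometry in patients withdrawn before Week 12, then makes it optional once drug has stopped, which does not fit the treatment-policy estimand

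*Protocol*

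**What the plan says.** **Protocol 7.3.1.1, opening rule.** For patients withdrawn before completing Week 12, "every attempt should be made to have the patient complete the 12-hour spirometry procedures and the ECG procedures at the early termination/withdrawal visit". The exceptions are withdrawal of consent and safety reasons that rule the assessment out. Being off drug is not an exception.

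**Protocol 7.3.1.1, the two groups.** On drug: "Patients who have continued administration of their blinded study medication should complete the spirometry and ECG procedures as follows". Off drug: patients who stopped "prior to the early termination/withdrawal visit may optionally complete spirometry and ECG assessments at the early termination visit", provided the Week 12 assessments are not already done. The section sets out an undosed series from 0 to 12 hours for this group.

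**Protocol 7.1.** Unless the reason is COVID-19, a patient who must stop drug should complete the "assessments described in Section 7.3 as soon as possible". No option is mentioned.

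**Protocol 7.2, patients who stay in the study.** "Ideally, patients who have permanently discontinued blinded study medication will continue to attend scheduled clinic visits and complete important efficacy and safety assessments". Option 7.2.1 keeps spirometry on the normal schedule. Under 7.2.2, contact is by phone and clinic spirometry is confined to one visit: "In addition, the patient returns to the clinic at Week 24 to complete the following assessments". Option 7.2.3 is phone only.

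**Analysis.** The intercurrent-event strategy for the primary estimand (SAP 2.5) is "Regardless of whether the patient discontinues treatment prematurely and regardless of major protocol deviation, as per the Treatment Policy strategy". Protocol 9.4.1 ranks the sources for a missing primary value: "Primarily imputation will be based on data collected at visits performed after treatment withdrawal or at early termination visits even if outside visit window". For patients who leave the study, SAP 6.4 maps an end-of-study AUC0-12h to Week 12 if it falls after Day 1 and no later than Day 95. What is still missing is multiply imputed under MAR (SAP 16.1.2).

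**The concern.** A treatment-policy estimand needs outcomes after drug is stopped. The optional wording weakens the instruction to collect the primary measurement in exactly the patients whose off-drug outcome the estimand includes, while the instruction for on-drug patients stays firm.

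If an off-drug patient skips the series and has no later Week 12 visit, the value is imputed. The SAP 16.1.2 model holds treatment, region, the two strata, baseline FEV1 and Week 12 AUC0-12h, with nothing to separate on-drug from off-drug patients. The imputed value then resembles the observed patients in the same arm. If those are mainly on drug and benefit is lost on stopping, the ensifentrine mean is too high for the stated estimand.

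**Working it through.** **1. The plan's own figure.** Protocol 9.2 gives SD 250 mL, 500 vs 300 evaluable patients, two-sided 5%, and 90% power for 59 mL.

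SE = 250 × √(1/300 + 1/500) = 18.26 mL. Power = Φ(59/18.26 − 1.96) = Φ(1.27) = 0.898. This reproduces the stated 90%; nothing here disputes the sample size.

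**2. Who is exposed.**

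| Off-drug patient before Week 12 | Route to a primary value |
|---|---|
| Stays, full visits (7.2) or 7.2.1 | Scheduled Week 12 series |
| Stays under 7.2.2 or 7.2.3 | Early termination series only (optional) |
| Leaves the study | Early termination series only (optional) |

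**3. Size of the gap.** Let f be the share of the ensifentrine arm off drug by Week 12, q the share of those measured, and e the effect in off-drug patients. On-drug effect is 59 mL. Assume that stopping does not change the placebo mean.

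- Treatment-policy effect: T = 59(1 − f) + e·f
- MAR estimate: M = [59(1 − f) + e·f·q] / [(1 − f) + f·q]
- Overstatement: M − T. With e = 0 this equals 59·K, where K = (1 − f)·f(1 − q) / [1 − f(1 − q)].

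The documents give none of f, q or e, so the rows below are assumptions.

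| f | Unmeasured (1 − q) | M − T, e = 0 | M − T, e = 29.5 mL |
|---|---|---|---|
| 5% | 25% | 0.7 mL | 0.4 mL |
| 10% | 50% | 2.8 mL | 1.4 mL |
| 15% | 75% | 6.4 mL | 3.2 mL |

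Middle row, e = 0: K = 0.90 × 0.05 / 0.95 = 0.0474, and 59 × 0.0474 = 2.8 mL. That is 2.8/59 = 5% of the planned effect and 2.8/18.26 = 0.15 SE. If every off-drug patient is measured (q = 1), the gap is 0.

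**4. The placebo arm.** The same option applies to placebo. With equal f and q in both arms, the net gap is K × (D_E − D_P), where D is the continuer-minus-stopper difference within an arm. With D_E = 59 and D_P = 0 the middle case gives 2.8 mL. With D_P = 29.5 it gives 0.0474 × 29.5 = 1.4 mL. With D_P = 59 it gives 0. If ensifentrine stoppers shared the same poorer prognosis, D_E would rise as well and the offset would shrink.

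**5. Would the series be usable?** SAP 16.1.1.1 does not calculate the AUC without a pre-dose measurement, defined as the latest value within 40 minutes before dosing. An undosed patient has a 0-hour value and no dose. The SAP does not say that this value qualifies, so a completed off-drug series could still be set to missing.

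**The case against.** The two sentences can be read together: the site tries, and the off-drug patient may decline. Other text supports collection. Section 7.3.1 says patients who cannot stay on drug should still attend the early termination visit, and the Schedule of Activities marks the 0-12 hour series at that visit. Patients are also asked to stay on drug until that visit where possible, which shrinks the off-drug group. The main route for off-drug data is continued attendance under 7.2, and a real Week 12 value serves the estimand better than an early one mapped to Week 12. The SAP also plans opposite-arm average imputation, a tipping-point analysis and observed-data analyses. Optional testing in patients who may just have had an exacerbation or adverse event is a defensible choice.

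Much of this stands, and it limits the point to the last two rows of the first table. It does not remove it. The opening rule already protects patients through its consent and safety exceptions, and a site reading the off-drug paragraph is told that the series is optional. The sensitivity analyses show whether the conclusion depends on the missing values, but they do not recover them.

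A reader might infer a larger bias by multiplying shares by the 87 mL seen in CO-205, for example 0.15 × 0.75 × 87 = 9.8 mL. The documents do not support that. The 87 mL is a Week 4 result on top of tiotropium, whereas background LAMA or LABA use is capped at 50% here. The simple product is also not the MAR gap, because measured off-drug patients stay among those who inform the imputation.

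**Conclusion.** The inconsistency in 7.3.1.1 is real and touches the primary endpoint. It also sits badly with 7.1 and with the treatment-policy estimand. Its likely size is modest: 2.8 mL in the middle case and 0.7 to 6.4 mL across the assumed range, or about 0.04 to 0.35 SE. These figures rest on assumed stopping and skipping rates, complete loss of benefit off drug, and placebo stoppers who do no worse than placebo continuers.

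A reader might go further and conclude that the primary estimate is biased upwards, or that early termination values come mostly from on-drug patients. Neither follows. The documents weaken the requirement to collect; they do not report what was collected. The net direction depends on stopping, measurement and prognosis in both arms. This is a cheap improvement.

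**What to change.** 1. **Protocol 7.3.1.1.** Reconcile the opening rule, the off-drug paragraph and 7.1 by giving spirometry in the off-drug paragraph the same every-attempt instruction, with the same consent and safety exceptions. ECG can stay optional. The undosed series and the dosing and withholding text stay unchanged.
2. **SAP 16.1.1.1.** State that, for a patient not dosed at the visit, the 0-hour value serves as the time-0 value, so that the AUC is calculated.

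The cost is one phrase in an amendment or clarification letter and one sentence in the SAP before unblinding. Some off-drug patients would have a longer final visit. The protocol change helps only patients not yet withdrawn; the SAP sentence also makes usable any undosed series already collected. Patients who decline or withdraw consent will still be missing, so the planned sensitivity analyses remain necessary.

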7.3.1.2 Single 12-Lead ECG

Patients who early term/withdraw after Week 12 and are not completing either the pre-dose and 1.5-hour or the 0-hour and 1.5-hour ECG assessments described in Section 7.3.1.1 will complete a single 12-lead ECG as per Section 8.4.2.

7.4 Lost to Follow-up

A patient will be considered lost to follow-up if he or she repeatedly fails to return for scheduled visits and is unable to be contacted by the study center.

The following actions must be taken if a patient fails to return to the clinic for a required study visit:

- The study center must attempt to contact the patient and reschedule the missed visit as soon as possible and counsel the patient on the importance of maintaining the assigned visit schedule and ascertain whether the patient wishes to and/or should continue in the study.

- Before a patient is deemed lost to follow-up, the Investigator or designee must make every effort to regain contact with the patient (where possible, 3 telephone calls and, if necessary, a certified letter to the patient's last known mailing address or local equivalent methods). These contact attempts should be documented in the patient's medical record.
- Should the patient continue to be unreachable, he/she will be considered to have withdrawn from the study.

8.0 STUDY ASSESSMENTS AND PROCEDURES

- Patients may not complete any Screening Visit Procedures including the Spirometry Assessment unless all prohibited medications/therapy described in Section 6.7.3 have been withheld for the defined time interval.
- Study procedures and their timing are summarized in the SoA (Section 1.3).
- Protocol waivers or exemptions are not allowed.
- Immediate safety concerns should be discussed with the Sponsor immediately upon occurrence or awareness to determine if the patient should continue or discontinue blinded study medication.
- Adherence to the study design requirements, including those specified in the SoA, is essential and required for study conduct.
- All Screening evaluations must be completed and reviewed to confirm that potential patients meet all eligibility criteria. The Investigator will maintain a screening log to record details of all patients screened and to confirm eligibility or record reasons for Screening failure, as applicable.
- Procedures conducted as part of the patient's routine clinical management (eg, blood count) and obtained before signing of the ICF may be utilized for Screening or baseline purposes provided the procedures met the protocol-specified criteria and were performed within the time frame defined in the SoA.
- The maximum amount of blood collected from each patient over the duration of the study, including any extra assessments that may be required, will not exceed 300 mL. Repeat or unscheduled samples may be taken for safety reasons or for technical issues with the samples.
- See Section 5.6 for specific information to be collected for screen failures.

